## 11 Statistical considerations

### 11.1 Sample size

A total of 250 subjects, including at least 25 Japanese subjects will be randomized in a 1:1:1:1:1 ratio to 1 of the 5 treatment regimens outlined in Section 6.2.

The sample size is chosen, based on the results of a simulation. The simulation assessed the power to reject the null hypotheses included in the testing hierarchy specified in Section 11.3.6. Additionally, the simulation was used to discern, for which effect sizes, the trial would have approximately 50% power to detect a significant difference, in the mean percent change from baseline in EASI score at Week 16 between dose regimens 1 and 2, at the 5% significance level.

The percent change from baseline was simulated in a 4-step process. First, baseline EASI scores were obtained by resampling from a large phase 3 development program in moderate-to-severe AD. Next, the change from baseline was simulated for each subject under a multivariate normal assumption. The assumed mean change from baseline in EASI score from Week 1 to 16 was based on a component related to the effect of treatment, provided in Panel 14 for all 5 dose regimens and an effect related to the baseline EASI score for each assessment.

#### Panel 14: Assumed values for the mean change from baseline in EASI score from Week 1 to Week 16

	Wk 1	Wk 2	Wk 3	Wk 4	Wk 6	Wk 8	Wk 10	Wk 12	Wk 14	Wk 16
Dose regimen 1	-6.8	-10.3	-13.8	-17.3	-19.6	-18.8	-18.2	-17.8	-19.3	-20.7
Dose regimen 2	-5.0	-7.6	-10.2	-12.8	-14.5	-13.9	-13.5	-13.2	-14.3	-15.3
Dose regimen 3	-5.0	-6.8	-9.2	-11.5	-13.1	-12.5	-12.2	-11.9	-12.9	-13.8
Dose regimen 4	-3.3	-5.0	-6.6	-8.3	-9.4	-9.0	-8.8	-8.6	-9.3	-10.0
Placebo	-1.9	-3.8	-4.2	-4.6	-5.4	-3.8	-4.6	-5.4	-4.5	-3.5

Abbreviations: Wk = Week.

The assumptions for the placebo and dose regimen 2 groups are based on the observed data from the phase 2a proof-of-concept trial. Based on PK/PD modeling, it is anticipated that dose regimens 3 and 4 will retain approximately 90% and 65% of the mean change from baseline in EASI score observed for dose regimen █ in the phase █ trial. For dose regimen 1, the mean change from baseline in EASI score from Week 1 to Week 16 is assumed to have an additional reduction of 35% compared to dose regimen 2.

THIS DOCUMENT CONTAINS CONFIDENTIAL INFORMATION AND MUST NOT BE COPIED OR MADE AVAILABLE TO ANY THIRD PARTY WITHOUT THE PRIOR WRITTEN CONSENT OF THE LEO PHARMA GROUP

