The covariance matrices for the 5 dose regimens in the simulation were assumed to be equal and have a compound symmetry structure with variances equal to 111.0 and covariances equal to 32.5.

The third step was to ensure that the underlying EASI scores from Week 1 to 16 were within the range of the EASI score scale, which runs from [0,72]. This implies natural bounds for the individual simulated changes from baseline in EASI score, as they must lie within the interval, [-baseline score, 72-baseline score].

The final step was to derive the percent change from baseline in EASI score from Week 1 to Week 16, by dividing the simulated changes in baseline in EASI score from Week 1 to 16 by the subject's baseline EASI score.

The simulation further assumed that percentage of subjects withdrawing or experiencing an intercurrent event by Week 16 in dose regimens 1-4 and placebo arms are 20%, 20%, 30%, 40%, and 40%, respectively, the timing of which was assumed to be exponentially distributed.

To approximate the power, 1,000 data sets with 250 subjects were generated based on the randomization scheme. For each data set, 100 complete versions were generated by imputing missing data separately for each treatment arm. The baseline and all post-baseline EASI assessments were included in the imputation model. The imputed data sets were analyzed based on an ANCOVA model. The pooled estimate of the difference in the LSmean change from baseline, along with the associated 95% Cis and nominal p-values, were derived for each simulated data set by applying Rubin's rules to the estimates and standard errors from the ANCOVA analysis of the imputed datasets.

**Panel 15** provides the nominal power as well as the prioritized power based on the hierarchical testing procedure, to reject the null hypotheses testing the LEO 138559 dose regimens 1-4 versus placebo, with respect to the differences in the mean percent change in EASI score from baseline to Week 16.

THIS DOCUMENT CONTAINS CONFIDENTIAL INFORMATION AND MUST NOT BE COPIED OR MADE AVAILABLE TO ANY THIRD PARTY WITHOUT THE PRIOR WRITTEN CONSENT OF THE LEO PHARMA GROUP

**Panel 15: Approximate nominal and prioritized power for rejecting the null hypotheses including in the testing hierarchy, based on the results of the simulation**

Hypothesis	Nominal power	Prioritized power
Dose regimen 1 vs Placebo	~100%	~100%
Dose regimen 2 vs Placebo	99.1%	~99.1%
Dose regimen 3 vs Placebo	97.2%	~96.4%

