## 11.3 Statistical analysis

### 11.3.1 General principles

Baseline measurements are defined as the latest available observation at or prior to the date of the first IMP administration, unless otherwise specified.

All significance tests will be two-sided using the 5% significance level. All CIs will be presented with 95% degree of confidence, unless otherwise specified. LSmeans will be estimated using the observed margins for the FAS.

THIS DOCUMENT CONTAINS CONFIDENTIAL INFORMATION AND MUST NOT BE COPIED OR MADE AVAILABLE TO ANY THIRD PARTY WITHOUT THE PRIOR WRITTEN CONSENT OF THE LEO PHARMA GROUP

An observed-cases approach will be used for tabulations of data by visit (that is, involving only those subjects who attended each specific visit).

Categorical data will be summarized using the number and percentage of subjects in each category and treatment group. Continuous data will be summarized using the mean, SD, median, 1st quartile and 3rd quartile, minimum, and maximum values.

All the analyses specified in the protocol will be reviewed in relation to the blinded data actually obtained, and the SAP will be finalized before breaking the randomization code.

Any changes from the statistical analyses planned in this clinical trial protocol will be described and justified in a protocol amendment, the SAP and/or in the CTR, dependent on the type of change.

Unless otherwise stated, efficacy analyses will be performed based on the FAS, safety analyses will be based on the safety analysis set, and PK analyses will be based on the PK analysis set.

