## Panel 17: Statistical analysis of endpoints

Endpoint	Estimands to be analyzed
Percent change in EASI score from baseline to Week 16.	Primary estimand for continuous endpoints. Hypothetical supplementary estimand for continuous endpoints. Second supplementary estimand for continuous endpoints.
Achievement of EASI-50 at Week 16.	Primary estimand for binary endpoints. Supplementary estimand for binary endpoints.
Achievement of EASI-75 at Week 16.	Primary estimand for binary endpoints. Supplementary estimand for binary endpoints.
Achievement of EASI-90 at Week 16.	Primary estimand for binary endpoints. Supplementary estimand for binary endpoints.
Achievement of EASI-100 at Week 16.	Primary estimand for binary endpoints. Supplementary estimand for binary endpoints.
Change in EASI score from baseline to Week 16.	Primary estimand for continuous endpoints. Hypothetical supplementary estimand for continuous endpoints.
Change in SCORAD score from baseline to Week 16.	Primary estimand for continuous endpoints. Hypothetical supplementary estimand for continuous endpoints.
Percent change in SCORAD score from baseline to Week 16.	Primary estimand for continuous endpoints. Hypothetical supplementary estimand for continuous endpoints.
Achievement of vIGA-AD score of 0 (clear) or 1 (almost clear) at Week 16.	Primary estimand for binary endpoints. Supplementary estimand for binary endpoints.
Change in BSA from baseline to Week 16.	Primary estimand for continuous endpoints. Hypothetical supplementary estimand for continuous endpoints.
Percent change in BSA from baseline to Week 16.	Primary estimand for continuous endpoints. Hypothetical supplementary estimand for continuous endpoints.
Reduction of ADSD Worst █ score (weekly average) $\geq 4$ from baseline to Week 16.	Primary estimand for binary endpoints. Supplementary estimand for binary endpoints.
Change in DLQI (and individual domain scores) from baseline to Week 16.	Primary estimand for continuous endpoints. Hypothetical supplementary estimand for continuous endpoints.
Percent change in DLQI (and individual domain scores) from baseline to Week 16.	Primary estimand for continuous endpoints. Hypothetical supplementary estimand for continuous endpoints.
Change in POEM score (and individual item scores related to itch and sleep) from baseline to Week 16.	Primary estimand for continuous endpoints. Hypothetical supplementary estimand for continuous endpoints.

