#### **11.3.8.2 Analysis of primary estimand for binary endpoints**

Subjects receiving rescue treatment or who have permanently discontinued IMP due to lack of efficacy, or the occurrence of an AE related to worsening of AD, prior to the endpoint of interest, are defined as non-responders, reflecting an assumption that the occurrence of such intercurrent events indicates a failure of the randomized treatment.

Data observed after the permanent discontinuation of IMP for reasons besides lack of efficacy or the occurrence of an AE related to worsening of AD will be excluded from the analysis and treated as missing. Missing data and data treated as missing will be imputed using MI (100 iterations) under a MAR assumption within each treatment group. All subject-level data observed prior to the occurrence of an intercurrent event will be used to inform the imputation

THIS DOCUMENT CONTAINS CONFIDENTIAL INFORMATION AND MUST NOT BE COPIED OR MADE AVAILABLE TO ANY THIRD PARTY WITHOUT THE PRIOR WRITTEN CONSENT OF THE LEO PHARMA GROUP

models. Further details regarding the specification of the imputation models will be specified in the SAP.

The 100 complete datasets will be analyzed based on a logistic regression model, including treatment, baseline disease severity (vIGA-AD score at baseline), region (Japan, Other countries), prior use of biologics or systemic JAK inhibitors for AD (Yes/No) and the baseline value of the endpoint as a covariate. The logistic regression model will be used to estimate the risk, risk difference, and associated 95% CI based on the standardized estimator presented in Bartlett (80). For the analysis of the vIGA-AD responder endpoints, baseline disease severity will not be included as a covariate in the logistic regression model.

The pooled estimate of the risk difference, along with the associated 95% CIs and nominal p-values will be presented. Inference will be based on applying Rubin's rules to the estimates obtained from the analysis of the imputed data sets using the standardized estimator.

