### **11.3.9.3 Analysis of supplementary estimand for binary endpoints**

#### **Primary analysis**

All observed data will be included in the analysis, including data observed after the occurrence of intercurrent events.

Missing data will be imputed using MI (100 iterations) under a MAR assumption within each treatment group. All observed data will be used to inform the imputation model. Further details regarding the specification of the imputation models will be detailed in the SAP.

THIS DOCUMENT CONTAINS CONFIDENTIAL INFORMATION AND MUST NOT BE COPIED OR MADE AVAILABLE TO ANY THIRD PARTY WITHOUT THE PRIOR WRITTEN CONSENT OF THE LEO PHARMA GROUP

For each of the 100 complete datasets, the response will be analyzed using a logistic regression model including treatment, baseline disease severity (vIGA-AD score at baseline), region (Japan, Other countries), prior use of biologics or systemic JAK inhibitors for AD (Yes/No) and the baseline value of the endpoint as a covariate. For the analysis of the vIGA-AD responder endpoints, baseline disease severity will not be included as a factor in the logistic regression model.

The pooled estimate of the estimated risk differences and standard errors based on the standardized estimator presented in Bartlett (80), along with the associated 95% CIs and nominal p-values will be presented. Inference will be based on applying Rubin's rules to the estimates and standard errors from the analyses of the imputed datasets.

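### EASI-90 and EASI-100 are analyzed with unpenalized logistic regression and a Wald-type risk difference, although zero placebo responders is plausible and small counts make that interval too narrow

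*Combined protocol and SAP*

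**What the plan says.** Section 11.3.8.2 counts rescue, and stopping treatment for lack of efficacy or an AD-worsening adverse event, as non-response, and multiply imputes other missing data within arm. It then states: "The 100 complete datasets will be analyzed based on a logistic regression model". The model contains treatment, baseline vIGA-AD, region, prior biologic or systemic JAK inhibitor use, and the baseline value. The reported quantity is a standardized risk difference with 95% CI and nominal p-value, pooled by Rubin's rules.

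Panel 17 sends "Achievement of EASI-100 at Week 16" and EASI-90 through this method for both binary estimands. For the supplementary estimand, Section 11.3.9.3 says "the response will be analyzed using a logistic regression model including treatment, baseline disease severity". Section 11.3.8.2 also repeats the primary-estimand analysis at every protocol-defined visit. In its tipping-point analysis it fits the same logistic model to a single complete dataset when the imputed statuses do not vary. None of these places says what to do when an arm has no responders.

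**The concern.** EASI-90 and EASI-100 are demanding endpoints, and the plan expects little change on placebo. If no placebo subject responds, the likelihood has no finite maximum in the treatment coefficient. The fitted placebo risk goes to zero, and placebo adds almost nothing to the variance of the risk difference. The interval and nominal p-value then reflect essentially the active arm alone. The plan also does not say whether fits that fail to converge enter the pooling over 100 imputations. At stake is the reliability of the intervals and p-values for two exploratory responder endpoints.

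**Working it through.** **Inputs from the documents**
- Section 11.1: "A total of 250 subjects, including at least 25 Japanese subjects will be randomized in a 1:1:1:1:1 ratio", so 50 per arm.
- Panel 14, Week 16 mean change: -20.7, -15.3, -13.8 and -10.0 for regimens 1-4; -3.5 for placebo.
- Section 11.1: "variances equal to 111.0 and covariances equal to 32.5" (SD = √111 = 10.54). Of the simulated changes: "they must lie within the interval, [-baseline score, 72-baseline score", which places a point mass at EASI 0, i.e. EASI-100.
- Section 11.1: withdrawal or intercurrent event in 20%, 20%, 30%, 40% and (placebo) 40%. Section 5.2: baseline EASI at least 16.
- Section 11.3.1: "All significance tests will be two-sided using the 5% significance level".

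**Not given, so assumed over a range**
- Baseline EASI: 16 plus a gamma variable, cut at 72, mean/SD 24/6, 28/10, 32/13 or 35/14.
- Baseline slope: 0 to -0.6 per EASI point.
- Share of events counted as non-response: none to all.

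**1. Reproducing Panel 15.** Power = Φ(Δ / √[111(1/n₁ + 1/n₀)] - 1.96), with completers 40/40/35/30 vs 30.

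| Regimen vs placebo | Δ | Δ/SE | Power | Panel 15 |
|---|---|---|---|---|
| 1 | 17.2 | 17.2/2.545 = 6.76 | ~100% | ~100% |
| 2 | 11.8 | 11.8/2.545 = 4.64 | 99.6% | 99.1% |
| 3 | 10.3 | 10.3/2.621 = 3.93 | 97.6% | 97.2% |
| 4 | 6.5 | 6.5/2.720 = 2.39 | 66.6% | 67.4% |

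Regimen 1 vs 2 gives 63.0% against 49.7%, because the shortcut ignores the bound at EASI 0. The documents state no EASI-90 or EASI-100 rate.

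**2. Probability of zero placebo responders.** The same model gives placebo rates of 0.6-5.9% (EASI-90) and 0.3-4.1% (EASI-100). P(0 of 50) = (1 - p)^50; if all 40% of placebo events are non-response, p becomes 0.6p.

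| p | (1 - p)^50 | (1 - 0.6p)^50 |
|---|---|---|
| 0.3% | 86% | 91% |
| 0.6% | 74% | 83% |
| 4% | 13% | 30% |
| 6% | 5% | 16% |

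Across the assumptions, P(0 of 50) is 5-83% for EASI-90 and 13-91% for EASI-100. With no baseline slope, EASI-90 stays at 5-47%. At Week 1, with no events, it is 18-78% (EASI-90) and 33-88% (EASI-100) in the three settings run.

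**3. What zero responders does.** Take 4/50 vs 0/50. SE = √(0.08 × 0.92/50 + 0) = 0.0384, so the Wald CI is 0.5% to 15.5%, p = 0.037. The Newcombe CI is -0.6% to 18.8%; Fisher's exact p = 0.12. In simulated logistic fits with zero placebo responders, the coefficient was drifting to about -21 when iteration stopped. The standardized risk difference was finite in every one.

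**4. Coverage, unadjusted complete data.** All binomial(50) pairs enumerated:

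| Active vs placebo | Wald | Wald, placebo = 0 | Wald, placebo ≥ 1 | Newcombe |
|---|---|---|---|---|
| 3.5% vs 1% | 82.6% | 82.4% | 83.0% | 99.6% |
| 7.3% vs 1% | 88.2% | 87.9% | 88.7% | 98.4% |
| 20% vs 1% | 92.6% | 92.1% | 93.4% | 96.7% |

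**5. Coverage closer to the plan (simulation).**
- Standardized ML risk difference without imputation, Week 16: 43-95% across settings, lowest for regimen 4 where both arms are near zero. Newcombe: 95-100%. Firth with standardization: 93-100%.
- Standardized risk difference with imputation and Rubin's rules, half of events imputed (10 imputations, 400 trials, two settings): 93-97% for regimens 1-3, 98-100% for regimen 4.
- Unadjusted risk difference with imputation and Rubin's rules: about 93-97% with half of events imputed. With all events non-response, about 91-94% for regimens 1 and 3 and 76-93% for regimen 4.

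**The case against.** Three stronger readings are tempting, and the documents do not support them.

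A reader might infer that the analysis will simply fail. The plan reports a risk difference, not a coefficient, and the risk difference stays finite.

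A reader might infer that Section 11.1 makes zero placebo responders likely. It does not settle this: baseline EASI is resampled from an outside program, the baseline effect is unstated, and the bounded normal model was built to power a mean difference. Of the settings tried, the one closest to Panel 15 (baseline 32/13, slope -0.4) gives 69% and 82% with no events. Other settings also reproduce regimens 1-3, so this does not identify the rate.

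A reader might infer that the zero count itself causes the undercoverage. Step 4 shows coverage hardly changes with the placebo count (82.4% vs 83.0%). The cause is small counts; at 3.5% vs 1%, 59% of the misses have zero responders in both arms.

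It is also fair that the 83/88/93% figures are unadjusted and without imputation, and that imputing half the events gave close to nominal coverage. That protection comes from between-imputation variance. It shrinks if most placebo events are rescue or lack of efficacy, and probably at early visits, when fewer data should be missing. In the single-dataset tipping-point fits there is none.

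Finally, Section 11.3.1 finalizes the SAP before the code is broken, so a later data-driven choice is not a given. But Section 11.3.8.2 leaves imputation and tipping-point details to the SAP, not the main analysis model.

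**Conclusion.** The point holds, at modest size. The stated method suits EASI-90 and EASI-100 poorly, and a better one is readily available. Zero placebo responders is plausible rather than shown to be likely. Undercoverage runs from a few points where the active response is 20% to more than ten points where both rates are low, and regimen 4 is the most exposed. Its size under the planned analysis depends mainly on how many events are imputed rather than counted as non-response.

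The results rest on the assumed baseline distribution, slope and event split, on assumed covariate frequencies (Japan 10%, prior use 40%), and on a delta-method variance. Both endpoints are exploratory with nominal p-values. The primary ANCOVA and the testing hierarchy in Section 11.3.6 are unaffected.

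**What to change.** Before unblinding, specify for EASI-90 and EASI-100, at all visits, for both binary estimands and in the tipping-point analysis:

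1. Fit Firth-penalized logistic regression in each imputed dataset for every arm, standardize to the risk difference, and pool by Rubin's rules. State the variance formula.
2. Use no count-based switch. At placebo rates of 1-1.6%, a trigger of fewer than 5 responders in any arm would fire in about 99.9% of trials, and it is undefined when counts differ across 100 imputed datasets.
3. Report a score-type risk-difference interval (Newcombe or Miettinen-Nurminen) as a sensitivity analysis, with its pooling across imputations defined.

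Cost: a few lines of text and a little more programming. Intervals become somewhat wider. In an unadjusted two-arm model Firth estimates each risk as (y + 0.5)/(n + 1). A 1% placebo risk then has expectation (0.5 + 0.5)/51 = 2.0%, and the risk difference shrinks by the factor 50/51, about 2% in relative terms. The Firth coverage above was checked without imputation only, so a short simulation of the full procedure is worth running when the text is finalized.

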### **Sensitivity analysis**

A 2-dimensional tipping point sensitivity analysis will be performed for the binary endpoints related to EASI, vIGA-AD, and ADSD Worst █ score.

For each treatment comparison versus placebo, responder statuses that are either missing or treated as missing will be imputed for both arms across a range of response probabilities. The exact range, along with the number of imputations, imputation models, and the seeds will be specified in the SAP. The multiple imputed complete data sets for each point in the 2-dimensional tipping point analysis will be analyzed as specified for the primary analysis. For the cases where there is no variation in the imputed response statuses, the analysis will be conducted based on fitting the logistic regression model (as described earlier in this section) to a single complete data set. The p-values from the analysis of each point in the 2-dimensional tipping point analysis will be presented in a figure, along with any potentially identified tipping point (in this case a tipping line).

### **Supplementary analysis**

For the binary endpoints related to EASI, vIGA-AD and ADSD Worst █ score, the primary estimand will be analyzed for all protocol-defined visit weeks.

#### **11.3.8.3 Analysis of primary estimand for time-to-event endpoint**

##### **Primary analysis**

Let  $T$  represent the time from baseline to initiation of rescue treatment and  $T_{IE}$  represent the time from baseline to occurrence of permanent discontinuation of IMP or withdrawal from trial. The *while on treatment* estimand evaluates:

THIS DOCUMENT CONTAINS CONFIDENTIAL INFORMATION AND MUST NOT BE COPIED OR MADE AVAILABLE TO ANY THIRD PARTY WITHOUT THE PRIOR WRITTEN CONSENT OF THE LEO PHARMA GROUP

$$Pr(T < T_{IE} \wedge C_{admin})$$

where  $T_{IE} \wedge C_{admin}$  is the minimum of  $T_{IE}$  and the end of the treatment period (administrative censoring time), corresponding to Week 16. Since interest lies in estimating the time to initiating rescue treatment, the occurrence of permanent discontinuation of IMP or withdrawal from trial can be accounted for through the formulation of a competing risks model.

The null hypothesis,  $H_{0,i}: \lambda_{\text{LEO 138559, regimen } i}(t) = \lambda_{\text{placebo}}(t), \forall t \in (0,16)$ , where  $\lambda(t)$  denotes the sub-distribution hazard rate associated with the time-to-event endpoint at time  $t$  (measured in weeks) and  $i \in (1,2,3,4)$  denotes the LEO 138559 dose regimen, will be tested against the alternative,  $H_{A,i}: \lambda_{\text{LEO 138559, dosage regimen } i}(t) \neq \lambda_{\text{placebo}}(t)$  based on Gray's test, stratified by baseline disease severity (baseline vIGA-AD score), region (Japan, Other countries), and prior use of biologics or systemic JAK inhibitors for AD (Yes/No).

To quantify the magnitude of the potential treatment effect, the estimated cumulative incidence functions for the competing risks model will be presented for the treatment groups, based on the Aalen-Johansen estimator, along with 95% CIs.

